We will evaluate whether the weight based vitamin D loading protocol, when compared with usual care, results in:

1. Greater occurrence of vitamin D related adverse events (e.g. hypercalcemia, hypercalciuria)
2. Improved vitamin D axis functioning (e.g. active hormone levels, calcium metabolism)
3. Differences in blood measures of inflammation and innate immunity (e.g. CRP, procalcitonin)

Tertiary Objectives

If the dosing protocol evaluated as part of this dose evaluation RCT is successful we will subsequently undertake a multicentre phase III trial. For this reason the VITdAL-PICU pilot study will also explore a number of feasibility objectives:

1. Assess adherence and problems with our proposed treatment protocol (including blinding)
2. Assess the appropriateness of our eligibility criteria for the full trial
3. Estimate the rate of patient recruitment and understand barriers to recruitment

ELIGIBILITY CRITERIA

Inclusion Criteria

The inclusion criteria for this study are:

- (i) Admitted to ICU,
- (ii) Corrected gestational age > 37 weeks to age < 18 years,
- (iii) Expected ICU admission in excess of 48 hours, and will have access for bloodwork at 7 days (clinical bloodwork or lines)
- (iv) Blood 25(OH)D less than 50 nmol/L (regardless of prior approach to supplementation),

We have chosen to include children with a wide range of underlying diagnoses as vitamin D is a pleiotropic hormone important for the health and stress response of a many different organs and tissues^{13,14}. Regardless of inciting event, secondary pathophysiology involving the immune, cardiac, respiratory and renal systems is common during critical illness. Note – Premature infants are at increased risk for nephrocalcinosis and will require evaluation as part of a separate NICU based study.

Exclusion Criteria

Patients who meet any of the following criteria will be excluded:

- (i) Significant gastrointestinal disorder preventing enteral drug administration (e.g. necrotizing enterocolitis);
- (ii) Hypercalcemia (excluding transient abnormalities and those related to parenteral calcium administration for hypocalcemia);
- (iii) Confirmed or suspected William's syndrome;
- (iv) Patient known to have nephrolithiasis or Nephrocalcinosis;
- (v) Imminent plan for withdrawal of care or transfer to another ICU;
- (vi) Physician refusal;
- (vii) Previous enrollment in the study;
- (viii) Patient known to have granulomatous disease (tuberculosis or sarcoidosis),

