Note - Two published adult studies, and our pediatric study⁹⁸ have failed to demonstrate blood concentrations of 1,25(OH)₂D as a superior marker of vitamin D status in critically ill patients⁹⁹⁻¹⁰¹.

Note – If bloodwork cannot be obtained on day 7 ± 48 hours (e.g. no access to bloodwork, patient discharged), the patient's 25(OH)D level from the day 3 sample will be used for the primary outcome

Other outcome measures:

1. Vitamin D related adverse events – A statistically measurable difference in clinically significant adverse events between the loading dose and placebo arms is unlikely in a phase II study. Therefore, we will evaluate for potential toxicity using two well accepted surrogate outcome measures.
 - (i) Hypercalcemia – We will define hypercalcemia as an ionized calcium level above 1.40 mmol/L (children under 8 weeks as > 1.45 mmol/L)¹⁰²⁻¹⁰⁴.

- (ii) Hypercalciuria – We will identify hypercalciuria using calcium-creatinine ratios, defined using age specific norms and thresholds¹⁰⁴⁻¹⁰⁷.

As detailed in the DSMB section we will also evaluate for and report on the occurrence of serious adverse events that could potentially be related to vitamin D.

2. Vitamin D axis function – Improved signaling through the vitamin D axis will be evaluated through an evaluation of blood calcium, PTH and 1,25(OH)₂D. Change in immune function will be evaluated through inflammatory markers (C-reactive protein, procalcitonin) and antimicrobial peptide levels (cathelicidin)^{68,69,105}.
3. Feasibility - The pilot study will also allow us to evaluate protocol feasibility outcomes including protocol non-adherence, and study drop out. We will also preliminarily explore the feasibility of a subsequent multicentre phase III interventional study through an evaluation of the proposed eligibility criteria (i.e. can we predict ICU stay longer than 48 hours and the ability to obtain bloodwork at 7 days) and patient accrual rate. We will also assess our ability to maintain blinding by documenting the frequency of unblinding requests from the clinical care team and from the pharmacy.
4. Phase III trial outcomes - The pilot study will also allow us to assess potential outcomes for a phase III trial. These results will be used to better inform a sample size for subsequent phases of this research program. The Phase III trial outcomes that will be assessed are:
 - (i) Multiorgan dysfunction: (PELOD-2 score: days 0,3,7,14, and every 30 days until discharge or 90 days)

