Study participants will receive study drug (vitamin D or placebo) at enrollment. Study participants will be followed until hospital discharge (censored at 3 months following enrollment). Three months will be an adequate period to screen for potential side effects of rapid normalization of vitamin D status (hypercalcemia, hypercalciuria, nephrocalcinosis). Patients who are discharged from hospital before 90 days will be contacted by telephone on Day 90 to determine if they have been readmitted to a hospital, have been ill, or if they have experienced any symptoms that could be related to vitamin D toxicity since discharge from hospital. In the subsequent phase III trial, patients may be followed for a longer period to better understand long-term health and resource benefits. Certain participants may need to be followed for a longer period of time. If a patient's 25(OH)D level at the last test prior to hospital discharge is >200 nmol/L (rare), they will be discussed with Endocrinology. We expect that this will be very small percentage of patients.

Frequency and Duration of Follow-Up

Study participants will have blood collected as part of the screening and enrolment process (to determine vitamin D status eligibility) and on days 1, 2, 3 and 7, at the time of the specific triggers, and

at the time of hospital discharge. Urine samples will be collected at enrolment (Day 0), on days 3, 7, and at the time of hospital discharge. To inform the analysis plan for the phase III trial we will collect clinical relevant outcome data including: fluid administration, surgical procedures, progression and resolution of organ dysfunction, occurrence of adverse events, readiness for ICU discharge, length of hospital stay, survival status, and development of new morbidity at discharge (collected three times a week until discharge from hospital or 90 days). Additional information will be collected for patients who are discharged from hospital before 90 days including hospital readmission rate, and frequency of illness.

STUDY MEDICATION/INTERVENTION

Europharm® has agreed to provide both the vitamin D and placebo solutions at no cost. Post-randomization, the hospital pharmacy will provide both vitamin D and placebo solutions to the nursing staff for administration.

Study Medication Description

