hypercalcemia, hypercalciuria, nephrocalcinosis) will be compared between the two treatment groups using Fisher's exact or Chi-square. For the analysis of outcome measures that represent time to event (extubation, ICU discharge) we will apply the log rank test and generate Kaplan-meier curves. If randomization does not lead to equal distribution of important variables (e.g. weight) the above analysis will be expanded to regression modeling to allow for adjustment.

Notes – (1) Some uncertainty exists as to the appropriate 25(OH)D threshold for an ICU study of rapid normalization of vitamin D status. For example, the VITdAL-ICU trial by [name] and colleagues identified a statistically significant difference in mortality in the subgroup of patients with severe vitamin D deficiency (<30 nmol/l)³². Although there was no mortality benefit for the group of patients with 25(OH)D between 30 and 50 nmol/L these patients appeared to benefit in other ways (e.g. greater grip strength, perceived physical abilities). As literature could emerge further supporting either of these cut-offs, we will determine the proportion of eligible patients with 25(OH)D under 30 and 50 nmol/l. This will allow us to determine the feasibility of a phase III trial using either threshold. (2) It is also unclear how many patients will be ineligible as a result of their inability to take drug enterally. The study by [name] and colleagues³² report approximately 25% of screened patients were excluded due to gastrointestinal dysfunction. We have approached Europharm® about creation of an intravenous form of cholecalciferol. They have expressed a willingness to discuss, but only if further data could be provided demonstrating need.

Acceptance of question and feasibility of study - Information collected on screening, eligibility, baseline vitamin D levels, protocol non-adherence and blinding failures (i.e. requests to unblind by clinical care team) will be used to evaluate the feasibility of a phase III study evaluating rapid normalization of vitamin D in critically ill children. Accrual rate will also be reported, but given that this is a dose-evaluation pilot it will not be formally assessed as a feasibility outcome (with predefined targets defining acceptable).

Frequency of Analyses

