Follow up for the VITDAL-PICU ends at 90 days, hospital discharge or death (with the exception of those patients that are followed by nephrology or endocrinology after hospital discharge). Consequently, loss to follow-up will primarily relate to participant withdrawal or drop out and is anticipated to be negligible (< 5%). As most critically ill ICU patients have regular blood work (daily) we anticipate that in the absence of death there will be research blood and urine collected for 25(OH)D and calcium determination on the vast majority (> 95%) of patients on days 3 and 7. For our ongoing RCT of pre-operative supplementation in children with CHD, post-operative collection of research blood for the primary outcome is 100%.

Role of the Data Safety Monitoring Board

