The Data Safety Monitoring Board (DSMB) will be comprised of two clinical experts and a biostatistician or clinical epidemiologist. Terms of Reference will be created for the DSMB and approved by all DSMB members and the Principal Investigator before recruitment commences. The DSMB will function independently and at arm's length from the Study investigators and the Steering Committee. The primary responsibilities of the DSMB are to: periodically review and evaluate the accumulated study data for participant safety; make recommendations to the Steering Committee based on these reviews regarding the continuation, modification or termination of the trial; and comment on the relevance of new external published data from other trials that may impact on patient safety or efficacy of the study treatments. The DSMB will meet and review 25(OH)D and safety data after 15, 30 and 52 participants have reached Day 7 of study enrolment. Alternatively, reviews will be conducted at least yearly. Specifically, the DSMB will review the percentage of participants meeting target 25(OH)D, those exceeding 200 and 250 nmol/L, and the occurrence of vitamin D related adverse events (hypercalciuria, hypercalcemia), and serious adverse events potentially related to study drug. With the exception of the 25(OH)D results, the DSMB will initially be blinded to study group allocation for safety data and any clinical or biochemical outcome data requested. However, the DSMB will also be provided with the group identity codes under separate cover so that they can evaluate the data with knowledge of treatment group if desired. If safety concerns arise, more frequent meetings will be initiated, and the trial may be terminated. The DSMB Chair can also request a full meeting at any time. The DSMB Chair will receive immediate notification and reports of serious adverse events determined to be related to the study drug. In addition, the DSMB Chair will receive a report for all deaths and all requirements for renal replacement therapy, regardless of whether they are thought to be related to the VITdAL-PICU study.

Adaptive design and stopping rules

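### Time to extubation and ICU discharge: Kaplan-Meier curves without death as a competing event would, under the default of censoring deaths, overstate the proportion extubated or discharged

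*Combined protocol and SAP*

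**What the plan says.** Under Statistical Plan, Analyses, the paragraph on vitamin D axis, adverse events and clinical outcomes names extubation and ICU discharge as the time-to-event measures. The whole method is "we will apply the log rank test and generate Kaplan-meier curves". Neither competing risks nor cumulative incidence is mentioned anywhere.

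The follow-up rules are in two places. Loss of Follow-Up states: "Follow up for the VITDAL-PICU ends at 90 days, hospital discharge or death". Study Duration and 90 Day Follow-Up state censoring at three months (90 days) from enrolment. That is the only censoring rule written down, and it does not mention death.

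Deaths are foreseen. Under Role of the Data Safety Monitoring Board, "the DSMB Chair will receive a report for all deaths", and the Exclusion Criteria remove children with an "Imminent plan for withdrawal of care or transfer to another ICU", which lowers the number of deaths without removing them. Survival status is collected: Frequency and Duration of Follow-Up lists "readiness for ICU discharge, length of hospital stay, survival status" among the data meant to inform the phase III analysis plan.

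Study Endpoints, Other outcome measures, item 4, lists two candidate phase III outcomes: PELOD-2 and readiness for PICU discharge. Of these it says: "These results will be used to better inform a sample size for subsequent phases of this research program".

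**The concern.** A child who dies in the ICU cannot later be discharged alive, and one who dies while ventilated cannot later be extubated. Kaplan-Meier treats a censored child as still able to have the event, at the same rate as those who remain under observation. If deaths are censored, the estimator redistributes their share to the survivors, and one minus Kaplan-Meier rises towards 100% whatever the mortality.

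Death is also likely to be the main source of censoring before day 90. Withdrawal is expected to be negligible (under 5%), and hospital discharge does not come before ICU discharge.

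At stake is the description of clinical course in each arm. The plotted proportions would be too high, and an arm with more deaths would not look worse on the discharge curve. The same method could also be carried into a larger trial, where the sampling error shrinks but this bias does not.

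**Working it through.** The plan gives no event count, hazard ratio, power or mortality for these analyses, so there is no figure of its own to reproduce. The adult mortality rates in the background section come from a different population and are not used.

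**Inputs.** From the documents: at most 67 patients; 40 and 20 per arm in Sample Size; 2:1 allocation; significance level 0.05; follow-up to day 90. Assumed: mortality m of 2% to 10%, and a constant discharge hazard L1 of 0.07 to 0.15 per day. Mortality of 2% to 10% among 67 patients means about 1.3 to 6.7 deaths (67 × 0.02 to 67 × 0.10).

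**Formulas.** With constant cause-specific hazards, the death hazard is L2 = L1 × m/(1 − m).

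- One minus Kaplan-Meier with deaths censored: 1 − exp(−L1·t).
- True cumulative proportion discharged: (1 − m) × [1 − exp(−(L1 + L2)·t)].
- The overstatement is the first minus the second.

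**Worked case: m = 5%, L1 = 0.10, day 28.** L2 = 0.10 × 0.05/0.95 = 0.00526. The first expression is 1 − exp(−2.8) = 93.9%. The second is 0.95 × [1 − exp(−2.947)] = 90.0%. The gap is 3.9 points. By day 90 the two figures are 100.0% and 95.0%, a gap of 5.0 points.

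**Overstatement in percentage points, day 28 / day 90:**

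| Mortality | L1 = 0.07 | L1 = 0.10 | L1 = 0.15 |
|---|---|---|---|
| 2% | 1.2 / 2.0 | 1.5 / 2.0 | 1.8 / 2.0 |
| 5% | 3.0 / 4.9 | 3.9 / 5.0 | 4.6 / 5.0 |
| 10% | 6.1 / 9.9 | 7.9 / 10.0 | 9.3 / 10.0 |

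**Finite sample.** In 3,000 simulated trials of 67 patients with L1 = 0.10, censoring deaths gave a mean day-28 figure of 94.0% at 2%, 5% and 10% mortality alike. Keeping deaths in the risk set to day 90 as non-events gave 92.4%, 90.0% and 86.0%, which equal the true cumulative incidence. The standard error of the day-28 estimate was about 3 points for all 67. Scaled to single arms it is roughly 3.0 × √(67/40) = 3.9 points and 3.0 × √(67/20) = 5.5 points.

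**Log-rank test.** With deaths censored, equal discharge hazards in both arms, 40 versus 20 patients and 3,000 runs, the test rejected as follows:

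- 5.2% with mortality 5% in both arms
- 6.1% with 3% (treatment) versus 10% (placebo)
- 5.7% with 10% (treatment) versus 3% (placebo)

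The Monte Carlo error is about 0.4 points. The test stays close to nominal for the cause-specific hazard, even though in the last two settings the true proportions discharged by day 90 are 97% and 90%.

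**The case against.** The strongest reply is that censoring at death is written nowhere. Kaplan-Meier and log-rank are not wrong in themselves: if deaths are kept as non-events to day 90, the same methods give no bias. That stands, and the point is therefore conditional. But follow-up ends at death and no other rule is given, so an analyst following the text would most naturally censor on that date.

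Three stronger readings are tempting, and the documents do not support them.

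- **A reader might infer that the log-rank test is invalid.** It is not. With deaths censored it tests the cause-specific hazard, and choosing Gray's test instead is a choice of estimand.
- **A reader might infer that these curves will set the phase III sample size.** The sentence on sample size governs two outcomes, PELOD-2 and readiness for PICU discharge. Extubation is not listed, and readiness is not the same as actual discharge.
- **A reader might infer that mortality will differ by arm because a survival effect is hypothesised.** The pilot hypothesis concerns rapid and safe normalisation of vitamin D. The phase III hypothesis speaks of patient outcomes and spending in general. The mortality signals come from an adult trial, so a bias that differs by arm is possible here but conjectural.

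The size is also modest. At L1 = 0.10 the median time to discharge is 6.9 days with deaths censored. The time by which half are truly discharged is 7.0, 7.1 or 7.3 days at 3%, 5% or 10% mortality. Survival status is already collected, so deaths could be read alongside the curves, although the plan does not say they will be.

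**Conclusion.** The point holds as a minor one. The plan uses Kaplan-Meier for two events that death precludes and does not treat death as a competing event. If deaths are censored at their date, the curves overstate the cumulative proportion discharged or extubated by about 1 to 9 points at day 28, and by about the mortality rate at day 90. These figures rest on assumed mortality of 2% to 10%, an assumed constant discharge hazard of 0.07 to 0.15 per day, and censoring at death, which the documents imply but do not state. They were computed for discharge; for extubation the mechanism is the same, but no extubation rate was modelled.

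At 2% mortality the day-28 gap is below the standard error at 67 patients; at 10% it is about two to three times the pooled standard error. The problem lies in the curves, not in the validity of the log-rank test, which does not compare cumulative proportions. The primary outcome, the 50% threshold for proceeding to phase III and the stopping rules for the primary outcome do not depend on these analyses.

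**What to change.** In the Analyses section, replace the Kaplan-Meier curves for extubation and ICU discharge with cumulative incidence curves that treat death as a competing event. Alternatively, keep children who die in the risk set as non-events to day 90. The two are equivalent when nobody else is censored before day 90, and nearly so with the few withdrawals expected. State that any log-rank test with deaths censored compares cause-specific hazards. If a comparison of cumulative proportions is wanted, name Gray's test. Report the number of deaths by arm beside the curves.

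The cost is one or two sentences and slightly more analysis work. Survival status is already collected and SAS is already the named software. Sample size, data collection and the primary analysis do not change.

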As there is little experience with weight based enteral vitamin D loading therapy in critically ill children we will plan for interim safety analysis after 15, 30 and 52 patients. After review of the 25(OH)D levels and adverse event data, the Data and Safety Monitoring Committee will be empowered to provide recommendations on stopping the trial or adjusting both the dosing regimen.

Subgroup Analyses

We will evaluate biochemical and clinical outcomes within three different subgroups. First, we will evaluate initial 25(OH)D response in the group of patients under and over 40 kg. Second, we will evaluate and compare changes in biochemistry and clinical measures separately for the groups with starting 25(OH)D above and below 30 nmol/L. Third, we will evaluate and compare 25(OH)D response and clinical measures separately for newborns (age < 30 days) versus older children (age > 30 days).

Feasibility of Recruitment

The planned recruitment rate is up to 67 patients. At CHEO we have between 500 and 600 PICU admissions per year. Of these, we anticipate that up to 50% of patients will either not be eligible, the physician will refuse, or the parents/caregivers will be unavailable or not willing to speak with research staff. Based on both our experience with vitamin D RCTs and previously published work on factors affecting consent in PICU studies in Canada, we anticipate that 50% (n=125, 10/month) of those approached will agree to participate¹¹¹. Of those that choose to participate we anticipate that approximately 50% (n=67, ~5 per month) will be eligible for randomization based on a 25(OH)D under 50 nmol/L. Recruitment rates are difficult to predict, and are frequently slower than expected. Consequently, we will allow up to 2 years for recruitment into this dose evaluation study. The recruitment rate will be enhanced with expansion of the study to the international sites and to the

NICU at CHEO. Recruitment through CVS, and alternate consent procedures for measuring vitamin D during screening will also improve recruitment rate (see Appendix K and Appendix L for Gantt timeline of this study and of the overall research program).

Loss of Follow-Up

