To ensure that we are not enrolling patients unnecessarily, it was decided at the Sept 8, 2015 Steering committee meeting that the DSMB also review the 25(OH)D primary outcome data after 30 and 52 patients have completed all study procedures (primary outcome data will not be reviewed after 15 patients). The following criteria will be used to determine whether the trial should be stopped early for the primary outcome.

- Proportion achieving 25(OH)D \geq 75 nmol/L
 - After 30 participants: Point estimate of \geq 90% (lower confidence interval would be approximately 75%)

- After 52 participants: Point estimate of >75% (lower confidence interval would be approximately 60%)

*If the DSMB was to see a signal in the SAE or vitamin D related adverse event data and felt that enrolling another 15 participants would help resolve whether the difference could be real they could recommend against stopping.

- Participants achieving potentially toxic levels
 - If more than 10% of study participants achieved 25(OH)D above 250 nmol/L, even in the absence of clinical sequelae, we will consider modifying the loading dose downward (these cases would be reviewed for signs of biochemical or clinical toxicity by the DSMB).

COST-EFFECTIVENESS SUB-STUDY

As part of the full phase III VITdAL-PICU trial we do intend to perform a cost effectiveness sub-study. A recently funded and active research project (DEMAND-PICU Study) by one of our co-applicants, [name], seeks to determine the costs associated with critical illness. These costs have not been previously documented in Canada, and will include those related to hospital (base rate, nursing ratios, etc.), patient (ECMO, dialysis, surgery, imaging, etc.) and family factors (distance from home, travel, hotel expenses). We anticipate the results of this study to be available well prior to the phase III trial. If funding for our pilot is secured and additional information is required, we will collect data as part of the VITdAL-PICU.

During the current phase II study, resource utilization data collected as part of the REB approved DEMAND-PICU study (REB no. 14/211X and 14/191X) will be linked to patients enrolled in VITdAL-PICU at CHEO to perform a pilot cost effectiveness sub-study. Data collection for the DEMAND-PICU study will run until February 2016, after which time we will continue to collect the same resource utilization data for VITdAL-PICU patients (if funding permits).

PARTICIPATING CENTRES

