Upon recognition of a reportable SAE, the site study staff will contact the Study Coordinator, who will contact the Principal Investigator and the Data Monitoring & Safety Committee (DMSC) Chair to alert them to forthcoming documentation. The site study staff will complete the reporting form and any outstanding case report forms (CRFs) for that patient within 3 days and send them to the Study Coordinator along with all relevant clinical notes (including all physicians' and nurses' notes, relevant diagnostic test results, surgical and other intervention reports). The Study Coordinator will collate these documents into a detailed report for distribution to the Principal Investigator and DMSC Chair within 5 days of becoming aware. These notes will be previewed by the Study Coordinator to ensure that they do not contain sensitive or confidential patient information, in accordance with PHIPA requirements.

After reviewing the clinical notes and CRFs, the DMSC chair will determine whether immediate input from other DMSC members is required and will contact them as needed. The DMSC will send their determinations to the Principal Investigator. Final determinations of the DMSC will be entered onto the relevant case report form, and into the database. The DMSC will also review aggregate SAEs and RUSARs after 30 and after 52 patients have received their initial loading dose. At this time, the DMSC will recommend to the VITdAL-PICU Steering Committee whether to (a) continue patient enrolment, (b) suspend enrolment until careful review by the Steering Committee, or (c) whether more information is required before a recommendation can be made. Furthermore, we will be reporting to regulatory bodies, all life threatening, fatal and all other serious adverse drug reactions potentially related to enrolment in VITdAL-PICU (as previously listed).

Examples of expected morbidities or complications of critical illness:

- Requirement for ventilator support
- Failed extubation
- Nosocomial infections

- Respiratory arrest
- Cardiac arrhythmias
- Unstable blood pressure
- Organ failure
- Myocardial infarction
- Presence of the following abnormal laboratory values:
 - hypoglycemia
 - hyperglycemia
 - hypocalcemia
 - hyponatremia
 - hypernatremia
 - hyperchloraemia
 - hypochloraemia
 - metabolic alkalosis (elevated bicarbonate)
 - metabolic acidosis (low bicarbonate)
 - lactic acidosis
 - hypokalemia
 - hypomagnesemia
 - Hypermagnesemia
 - Hypophosphatemia
 - Hyperphosphatemia

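### The sections disagree on what the DSMB sees at the 15-participant look and on what triggers each look; one reconciled table of looks is needed

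*Combined protocol and SAP*

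**What the plan says.** Four sections of the combined protocol and SAP set the interim looks, and two more govern when 25(OH)D is measured.

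- *Frequency of Analyses*: "we will plan for interim safety analysis after 15, 30 and 52 patients". The committee acts on two kinds of data: "After review of the 25(OH)D levels and adverse event data, the Data and Safety Monitoring Committee will be empowered".
- *Role of the Data Safety Monitoring Board*: "The DSMB will meet and review 25(OH)D and safety data after 15, 30 and 52 participants have reached Day 7 of study enrolment". The content is spelled out: "the DSMB will review the percentage of participants meeting target 25(OH)D, those exceeding 200 and 250 nmol/L", together with hypercalcemia, hypercalciuria and SAEs potentially related to study drug.
- *Adaptive design and stopping rules*: the board is to "review the 25(OH)D primary outcome data after 30 and 52 patients have completed all study procedures", with the qualification that "primary outcome data will not be reviewed after 15 patients". A separate bullet covers high levels ("If more than 10% of study participants achieved 25(OH)D above 250 nmol/L, even in the absence of clinical sequelae") and names no look.
- *Documentation, Monitoring, and Reporting of Adverse Events*: "The DMSC will also review aggregate SAEs and RUSARs after 30 and after 52 patients have received their initial loading dose". The recommendation to continue or suspend enrolment is attached to those reviews.
- *Blood and Urine Sampling* has the research samples assayed for 25(OH)D at study close-out. *Appendix I* has sub-site Day 1, 2, 3, 7 and post-intervention samples stored and sent to the coordinating centre. Only the screening and discharge levels are read in real time.

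The committee has three names across these sections (DSMB, Data and Safety Monitoring Committee, DMSC). I take them to be one body.

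**The concern.** The first look is the earliest point at which anyone sees the accumulating data together. *Frequency of Analyses* justifies the looks by the limited experience with this kind of load in critically ill children. A board working from the protocol could not tell whether its first report should contain the percentage at target, the counts of high levels, or the aggregate SAEs. It also could not tell when the report falls due.

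The criterion for levels above 250 nmol/L is meant to apply even where no clinical effect is apparent, so calcium monitoring does not replace it. If Day 3 and Day 7 samples wait in a freezer until close-out, a high early level may be seen by nobody before a look, and the look itself would have no such value to show.

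**Working it through.** **1. The sections side by side**

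| Section | Looks | Trigger | 25(OH)D at 15? | Aggregate SAEs at 15? |
|---|---|---|---|---|
| Frequency of Analyses | 15, 30, 52 | number of patients, no time point | yes, levels | adverse event data, yes |
| Role of the DSMB | 15, 30, 52 | Day 7 reached | yes: % at target, above 200, above 250 | yes, potentially related SAEs |
| Adaptive design and stopping rules | 30, 52 | all study procedures completed | primary outcome no; 250 criterion tied to no look | not addressed |
| Documentation, Monitoring, and Reporting of AEs | 30, 52 | initial loading dose received | not addressed | 15 not listed |

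The primary outcome in *Study Endpoints* is the proportion above 75 nmol/L. That is the same quantity as the percentage at target, so the second and third rows contradict each other even on the narrowest reading. The fourth row conflicts with the first two by omission.

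**2. Children given vitamin D at each look**

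Input: 2:1 allocation (*Study Summary*). Expected number = look size × 2/3.

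- 15 × 2/3 = 10 on vitamin D, 5 on placebo
- 30 × 2/3 = 20 on vitamin D, 10 on placebo
- Ratio 20/10 = 2

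With no events seen, the one-sided 95% upper bound on the true rate is 1 − 0.05^(1/n): 26% for n = 10 and 14% for n = 20.

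**3. Do the looks count total participants or vitamin D loads?**

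*Adaptive design and stopping rules* allows for 15 more participants after the 52 look: 52 + 15 = 67, the stated maximum total. The looks therefore count everyone enrolled.

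The plan's approximate lower confidence limits (75% and 60%) fit that reading. The Wald limit is 0.90 − 1.96√(0.90 × 0.10/20) = 77% at the 30 look, and 0.75 − 1.96√(0.75 × 0.25/35) = 61% at the 52 look. They do not settle it alone: Wilson limits for 27/30 and 39/52 are 74% and 62%. The sum to 67 does.

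**4. What a first look could show about levels above 250 nmol/L**

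The documents give no rate above 250, so the rates below are assumptions. Placebo children are taken to have no such levels. With 10 children on vitamin D, two events exceed 10% on either denominator (2/10 = 20%, 2/15 = 13%), and one does not.

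P(at least 2 of 10) = 1 − (1 − p)^10 − 10p(1 − p)^9

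| True rate p | At least 2 of 10 | At least 3 of 20 |
|---|---|---|
| 5% | 9% | 8% |
| 10% | 26% | 32% |
| 20% | 62% | 79% |

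At 30 participants the denominator matters. More than 10% means 3 events if only the vitamin D arm is counted (3/20), but 4 if all participants are (4/30). The bullet refers to study participants and does not say which.

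**5. Effect of the trigger**

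At the projected accrual of about 5 a month (*Feasibility of Recruitment*), waiting for Day 7 adds 5 × 7/30.4 ≈ 1 child. If completing all study procedures includes the Day 90 contact, which is an assumption, the wait adds 5 × 90/30.4 ≈ 15.

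**The case against.** The strongest answer is that the sections can be read together. *Adaptive design and stopping rules* adds a task for the board and withholds only primary outcome data at 15, in the setting of stopping early for the primary outcome. The 250 bullet stands apart from that, and *Analyses* likewise reports levels above 200 separately from the primary result. On this reading the counts above 200 and 250 remain at 15. The adverse event section says the committee will also review at 30 and 52; it does not say only then. This is a fair reading and it stands. A reader might infer that the first look has no check on high levels or on SAEs; the text does not go that far.

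The safeguards are also real. The board chair is notified at once of SAEs judged related, receives a report of every death and every need for renal replacement, and can call a full meeting at any time. Reportable SAEs reach the chair in a detailed report within 5 days. Blood and urine calcium are read in real time, and the discharge 25(OH)D is assayed to find levels above 200 nmol/L.

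A reader might also infer that the 52-patient SAE review could never happen, because it counts loading doses and the vitamin D arm stops at 40. The sum 52 + 15 = 67 rules that out.

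Finally, *Sample Size* assumes a mean near 110 nmol/L and an SD of at most 35, which puts 250 at (250 − 110)/35 = 4 SD above the mean. A 20% rate is far from what the plan expects.

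What the objection does not remove is the direct contradiction on the percentage at target, the missing 15 in the SAE section, the three triggers, or the assay timing.

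**Conclusion.** The inconsistency is real and should be corrected. Its consequence is conditional. Only if the two sections that omit 15 were taken to override the two that include it would the first aggregate check move from about 10 to about 20 children on vitamin D. That assumes exact 2:1 allocation at each look and refers to aggregate review alone; individual SAE reporting and calcium monitoring would continue. The detection probabilities of 9%, 26% and 62% illustrate what a first look could show at assumed rates of 5%, 10% and 20%. They are not estimates for this trial.

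The assay timing matters at least as much as the wording. Taken literally, assays at close-out would leave every interim look without Day 7 25(OH)D values, whatever the DSMB section promises. The sample size is unaffected.

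**What to change.** Reconcile *Frequency of Analyses*, *Role of the Data Safety Monitoring Board*, *Adaptive design and stopping rules*, *Documentation, Monitoring, and Reporting of Adverse Events*, *Blood and Urine Sampling* and *Appendix I* in one table of looks. For each look, give the trigger, the denominator and the data shown.

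- Show the counts above 200 and 250 nmol/L and the aggregate SAEs at 15, 30 and 52, as the DSMB section already lists.
- Omit only the percentage-at-target early-success review at 15.
- Use one trigger throughout, for example the DSMB section's participants reaching Day 7.
- State at which looks, and on which denominator, the criterion for levels above 250 nmol/L is read. The criterion itself, and any action on it, is for the sponsor to settle.
- Assay 25(OH)D in batches before each look, and amend the close-out wording to match.
- Use one name for the committee.

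The cost is protocol and charter wording, earlier batch assays and sample shipments timed to the looks. Because 25(OH)D values can reveal allocation, the batch results must reach the board without passing through blinded study staff.
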